STATISTICAL ANALYSIS PLAN

Effects of Stress Ball Use for Patients Undergoing Local Anesthesia in Ambulatory Surgery: A Randomized Controlled Trial

Official Study Title	Effects of Stress Ball Use for Patients Undergoing Local Anesthesia in Ambulatory Surgery: A Randomized Controlled Trial
ClinicalTrials.gov Identifier	NCT06742814
Document Type	Statistical Analysis Plan (SAP)
Sponsor / Institution	National Taiwan University Hospital, Hsin-Chu Branch, Taiwan
IRB Approval Number	202408018RIND (Research Ethics Committee D, National Taiwan University Hospital)
SAP Version	Version 1.0
Document Date	May 10, 2026

1. Background and Rationale

Outpatient surgery has expanded across surgical specialties and offers significant cost and efficiency advantages while maintaining acceptable short-term outcomes. In hand surgery, the wide-awake local anesthesia no tourniquet (WALANT) technique is increasingly used; patients remain fully conscious throughout the procedure without sedation or tourniquet, which may give rise to perioperative anxiety that is not always fully captured by self-report measures.

Heart rate variability (HRV) provides a continuous, objective, electrocardiography-derived index of autonomic regulation. The root mean square of successive differences (RMSSD) selectively reflects parasympathetic (vagally mediated) modulation and is well-suited to short-term clinical recordings. Stress ball use is a simple, low-cost, non-pharmacological strategy hypothesized to attenuate procedure-related stress through attentional distraction, active motor engagement, and tactile-proprioceptive input.

This trial evaluates whether intraoperative stress ball use enhances intraoperative parasympathetic modulation (indexed by lnRMSSD) and reduces perioperative anxiety and pain in patients undergoing outpatient hand surgery under local anesthesia without sedation. The trial was prospectively registered at ClinicalTrials.gov (NCT06742814) on December 15, 2024, prior to first-participant enrollment, and was approved by the Research Ethics Committee D of National Taiwan University Hospital (IRB No. 202408018RIND, approved August 2024).

2. Objectives and Hypotheses

2.1 Primary Objective

To evaluate the effect of intraoperative stress ball use on intraoperative HRV in patients undergoing outpatient hand surgery under local anesthesia without sedation, compared with standard perioperative care. (Prospectively specified in the ClinicalTrials.gov registration.)

2.2 Secondary Objectives

- To evaluate the effect of intraoperative stress ball use on postoperative state anxiety.
- To evaluate the effect of intraoperative stress ball use on postoperative pain intensity.

2.3 Hypotheses

Compared with the control group, the intervention group is hypothesized to demonstrate:

- H1 (Primary): Higher intraoperative lnRMSSD, reflecting enhanced parasympathetic modulation.
- H2 (Secondary): Lower postoperative state anxiety scores.
- H3 (Secondary): Lower postoperative pain intensity scores.

3. Study Design

This is a single-center, two-arm, parallel-group, statistician-blinded, randomized controlled trial reported in accordance with the CONSORT 2025 Statement (Hopewell et al., 2025). Participants are randomly allocated 1:1 to the intervention group (IG) or the control group (CG).

3.1 Eligibility Criteria

(Prospectively specified in the ClinicalTrials.gov registration and IRB-approved protocol.)

Inclusion Criteria

- Age ≥ 18 years and able to communicate in Mandarin or Taiwanese Hokkien.
- Scheduled to undergo outpatient hand surgery under local anesthesia.

Exclusion Criteria

- Use of anxiolytics or sedatives within one week prior to surgery.
- Concurrent bilateral hand surgery during the same operative session.
- Known cardiac arrhythmia or use of a cardiac pacemaker (rationale: ectopic beats and paced rhythms invalidate RMSSD-based HRV analysis).

3.2 Randomization and Blinding

Eligible participants are randomized 1:1 to IG or CG using a pre-generated computer randomization sequence (www.random.org). The allocation list is stored on a password-protected computer accessible only to the principal investigator. Participants are assigned strictly in the order in which they entered the study; no replacement or reassignment is permitted. Participant blinding is not feasible because of the nature of the intervention. Clinical staff present in the operating room are unaware of group assignments. Intraoperative HRV is recorded continuously and objectively by a portable ECG device and is therefore not subject to assessor interpretation. Statistical analyses are performed by an independent

statistician blinded to group allocation, with groups coded as “A” and “B” until the primary analysis is finalized.

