Per-Protocol Set	Participants in the FAS who: (a) received the allocated intervention as specified, (b) had no major protocol deviations, and (c) had complete primary outcome data with intraoperative HRV recordings meeting the R-wave validity criterion ($\geq 75\%$ valid beats). Used in supportive sensitivity

	analyses.
Safety Set	All randomized participants who underwent the surgical procedure, analyzed by the intervention actually received. Used for descriptive safety reporting only.

Major protocol deviations include: receipt of a non-allocated intervention, conversion to general or regional anesthesia, unplanned use of anxiolytic or sedative medication during the perioperative window, and HRV recording with < 75% valid R-waves.

6. Endpoints

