9.4 Secondary Analyses

Postoperative STAI-State and postoperative VAS are each analyzed using ANCOVA with the following model:

$$\text{Outcome_T3} = \beta_0 + \beta_1 \times \text{Group} + \beta_2 \times \text{Baseline} + \beta_3 \times \text{Age} + \beta_4 \times \text{Sex} + \epsilon$$

Where Baseline = STAI-State_T1 or VAS_T1, respectively. The homogeneity-of-slopes assumption is evaluated prior to each ANCOVA by testing the Group \times Baseline interaction. If violated for a secondary endpoint, the J–N procedure is applied analogously to the primary analysis. ANCOVA is selected for its robustness to deviations from normality given the sample size ($n > 30$ per group); where Shapiro–Wilk indicates substantial departure from normality, a non-parametric supportive analysis (Mann–Whitney U on change scores or rank-based ANCOVA) is reported.

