9.5 Sensitivity Analyses

- Per-Protocol analysis: the primary analysis (Path A or Path B) is repeated in the PP set.
- Unadjusted analysis: independent-samples t-test (or Mann–Whitney U) on T2 lnRMSSD without baseline or covariate adjustment.
- Covariate-minimal model: Path A or Path B fitted without age and sex, to assess covariate contribution.
- Influence diagnostics: standardized residuals from the primary model are inspected; analyses are repeated excluding observations with $|\text{standardized residual}| > 3$.

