This trial evaluates a low-risk, non-pharmacological intervention. No drug-related safety endpoints are prespecified. Adverse events potentially related to the surgical procedure or the intervention are recorded descriptively in the Safety Set. No inferential testing of safety outcomes is planned.

14. Specification Status of Analytical Elements

In the interest of full transparency, this section identifies the prospective specification status of each analytical element described in this SAP. Elements are categorized into three groups:

Analytical Element	Specification Status
Primary outcome (intraoperative HRV)	Prospectively specified in the ClinicalTrials.gov registration on December 15, 2024, prior to first-participant enrollment.
Secondary outcomes (STAI-State, VAS)	Prospectively specified in the ClinicalTrials.gov registration.
Directional hypothesis (IG > CG on InRMSSD)	Prospectively specified.
Eligibility criteria	Prospectively specified in the IRB-approved protocol and trial registration.
Randomization 1:1 with statistician blinding	Prospectively specified.
Sample size justification ($n = 74$)	Prospectively specified in the IRB-approved protocol.

ANCOVA as base analytic framework	Prospectively specified in the IRB-approved protocol.
Natural log transformation of RMSSD	Standard methodological convention (Laborde et al., 2017); applied prior to outcome modeling.
Inclusion of age and sex as covariates	Methodological refinement during the analysis phase, in line with standard recommendations for HRV research (Quigley et al., 2024). Applied uniformly to primary and secondary analyses prior to outcome modeling.
Johnson–Neyman procedure (Path B)	Methodological response to observed violation of the homogeneity-of-regression-slopes assumption (Hayes, 2022; Ji, 2016). The Johnson–Neyman procedure is the recognized standard analytical follow-up when the moderator is continuous and ANCOVA's homogeneity-of-slopes assumption is violated.
75% R-wave validity threshold	Methodological standard derived from Sheridan et al. (2020); applied uniformly to all participants.
Subgroup and sensitivity analyses	Exploratory; documented in this SAP.
Allocation concealment description	Clarified during manuscript preparation; reflects the actual procedure implemented since trial commencement, with no change in practice.

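### The statistician's mask is guaranteed only until the primary analysis is final, so per-protocol membership and the open choices of supportive test may be settled with the arms and the primary result known

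*Combined protocol and SAP*

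**What the plan says.** Section 3 describes the trial as statistician-blinded. Section 3.2 gives the detail: an independent statistician is "blinded to group allocation, with groups coded as “A” and “B” until the primary analysis is finalized". Section 14 lists statistician blinding as prospectively specified. The SAP describes no database lock, no masked data review and no date by which protocol deviations are classified.

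Section 5 admits to the Per-Protocol Set participants who "a) received the allocated intervention as specified, (b) had no major protocol deviations", and who also have complete primary data meeting the 75% R-wave criterion. It continues: "Major protocol deviations include: receipt of a non-allocated intervention", followed by other examples. Section 9.5 states the set's only use: "the primary analysis (Path A or Path B) is repeated in the PP set".

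For STAI-State and VAS, Section 9.4 specifies an ANCOVA with baseline, age and sex, and adds that "where Shapiro–Wilk indicates substantial departure from normality, a non-parametric supportive analysis (Mann–Whitney U on change scores or rank-based ANCOVA) is reported". For lnRMSSD, the unadjusted sensitivity analysis in Section 9.5 is a t-test with Mann–Whitney U in parentheses as an alternative, and no rule for choosing between them.

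**The concern.** A mask on the analyst protects the choices still open when the data are analysed. Here it may be lifted while several remain open, and by then the analyst can know which arm is which and what the primary result was.

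The per-protocol criterion is the most exposed. Section 3.3 asks the intervention arm to squeeze once every three seconds from the start of surgery to its completion while attending to the ball. The SAP sets no level of adherence that counts as having "received the allocated intervention as specified", and it describes no measurement of squeezing. Controls meet the criterion by resting an empty hand. The judgement therefore falls mainly on one arm, and a lenient or strict reading moves that arm alone.

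The per-protocol repeat will be read as evidence that the primary result is robust. If its membership could have been drawn with that result in view, it loses much of that value. The same holds, to a lesser degree, for a supportive test picked from two after both could be seen.

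**Working it through.** **1. Which analyses leave a choice, and is each covered by the stated mask?**

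| Analysis | Open choice | Covered by the mask in Section 3.2 |
|---|---|---|
| Primary lnRMSSD, FAS (9.3) | Outside this point | Yes |
| STAI-State and VAS, main ANCOVA (9.4) | Essentially none: model and population are stated | Not guaranteed, but little to exploit |
| STAI-State and VAS, non-parametric (9.4) | Substantial departure is undefined; two methods joined by or | Not guaranteed |
| Per-protocol repeat (9.5) | No adherence threshold; deviation list introduced by include | Not guaranteed |
| Unadjusted lnRMSSD (9.5) | t-test or Mann–Whitney U | Not guaranteed |
| Covariate-minimal model (9.5) | Essentially none | Not guaranteed, but little to exploit |
| Influence check (9.5) | Essentially none: cut-off of 3 is stated | Not guaranteed, but little to exploit |
| Subgroups (9.6) | Exploratory and descriptive | Not guaranteed |

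Two of the four sensitivity analyses in Section 9.5 carry real discretion, together with the non-parametric analysis in Section 9.4.

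**2. Size of a per-protocol selection effect.** The plan gives no figure for this, so what follows is an illustration. The inputs from Section 4 are 37 per group and a reference effect of 0.71 SD. The assumption is that values are roughly normal.

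- Worst case, the 3 lowest of 37 removed: p = 3/37 = 0.081, z = −1.40, φ(z) = 0.150. The mean of those remaining is φ(z)/(1 − p) = 0.150/0.919 = 0.163 SD. Simulation at n = 37 gives 0.157 SD, and 0.157/0.71 = 0.22 of the design effect.
- Three removed at random from the lower half: about 0.07 SD, and 0.07/0.71 = 0.10 of the design effect.
- Removal unrelated to outcome: about 0.

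These are shifts in the raw arm mean and ignore baseline adjustment.

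**3. Size of the test-choice effect.** This was simulated under no true effect, with 37 per group and 4,000 runs per scenario. The baseline–outcome correlation was 0.3 to 0.7 and the data normal or log-normal. None of these distributional inputs is in the documents.

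- Prespecified ANCOVA: rejects in about 4% to 5% of runs.
- Better of the two non-parametric methods: about 7% to 9%.
- Best of all three: about 8% to 10%.

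This inflation comes from choosing among results. An analyst who sees only A and B can also pick the smaller two-sided p-value, so a longer mask does not remove it. Naming the method, or reporting both, does.

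**4. Effect on the design.** None of this touches the evaluable sample of 64, the enrolment target of 74 or the primary alpha of 0.05.

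**The case against.** The strongest reply is that little of consequence is exposed. By the stated sequence, the primary result is final before the code is broken. The FAS is the primary population for all efficacy endpoints, the main secondary model is written down, and Section 11 labels the secondary endpoints supportive. Section 15 commits the publication to reporting the sensitivity and subgroup analyses. Section 3.2 also states the limit of the mask openly, so the label in Section 3 conceals nothing. All of this stands and it sets the scale of the point. It does not close the gap, because a commitment to report a per-protocol analysis does not say when or by whom its membership is fixed.

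Three stronger readings are tempting, and the documents do not support them.

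- A reader might infer that the mask is what protects STAI-State and VAS from participants who know their allocation. It is not. That bias arises when participants answer, and masking the analyst cannot remove it. Nor does the per-protocol set reach those endpoints, since Section 9.5 uses it only for lnRMSSD.
- A reader might infer from Section 14 that choices were in fact made unmasked. Section 14 calls the Johnson–Neyman step a "Methodological response to observed violation of the homogeneity-of-regression-slopes assumption", so some modelling preceded this SAP, dated May 10, 2026. But that step belongs to the primary analysis, which Section 3.2 places under the mask, and Section 14 says age and sex were applied before outcome modelling. The documents do not say when the code was broken.
- A reader might take 0.16 SD as the expected bias. It requires deliberate removal of exactly the lowest values. The documents do not say who classifies adherence and give no sign that this was done.

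**Conclusion.** The point holds in a limited form and is worth correcting. As written, the mask is guaranteed for the primary analysis only, while per-protocol membership and two choices of test are left open beyond it. The consequence falls on the per-protocol repeat of the lnRMSSD analysis, the non-parametric analyses of STAI-State and VAS, and the unadjusted lnRMSSD comparison. The primary FAS result and the main secondary ANCOVA are unaffected.

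The bias cannot be estimated from the documents. Under rough normality, the per-protocol shift runs from about 0 to a worst case of about 0.16 SD. The cost of an open test choice, about 7% to 9% false positives against about 4% to 5%, rests on the assumed correlations and distributions. The conclusion depends on neither figure: it follows from the end point stated in Section 3.2 and from the absence of any earlier date for fixing the open choices.

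**What to change.** - **Section 3.2:** keep the A/B code until all primary, secondary, sensitivity and subgroup analyses are finalized.
- **Section 5:** have someone without access to outcome data fix and date the per-protocol list before the code is broken, and pass the statistician only an in/out flag. That person needs to know the arms to apply the adherence criterion, which is why the task should be separate from the analysis.
- **Sections 9.4 and 9.5:** name one non-parametric method and one unadjusted test, or report both in each case.
- **If the code has already been broken or the list already set:** state when each happened, and limit the statistician-blinded description in Section 3 to the analyses actually run under the mask. Because Section 14 shows that some modelling has been done, a list fixed before any outcome model may no longer be possible. The SAP should then record what happened and not imply an order of events that did not occur.

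The cost is SAP wording, one dated list and a slightly later unmasking, with no change to sample size, alpha or endpoints. One drawback remains: if exclusions fall mostly in one group, the flag may hint at which code is the intervention arm.

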3.3 Intervention

All participants receive standard perioperative nursing care under local anesthesia using a mixture of 5 mL of 2% lidocaine, 5 mL of normal saline, and 0.1 mL of epinephrine (1 mg/mL), yielding an approximate final epinephrine concentration of 1:100,000, without tourniquet.

Following completion of all baseline assessments (T1), participants in the IG receive a commercially available soft foam stress ball (6 cm in diameter, moderate resistance) in their non-operative hand. A trained research assistant delivers standardized verbal instructions, asking participants to squeeze the ball rhythmically at a rate of once every three seconds while focusing attention on the ball, with the opportunity to practice before entering the operating room. The intervention commences at the initiation of surgery and continues until completion. Participants in the CG rest the non-operative hand naturally on the arm board without any object.

4. Sample Size Justification

(Prospectively specified in the IRB-approved protocol.)

Sample size was determined a priori using G*Power v3.1.9 ($\alpha = 0.05$ two-tailed; power = 0.80). Because no prior randomized controlled trial had examined the effect of stress ball use on HRV-based outcomes at the time of trial design, an effect size of Cohen's $d = 0.71$, derived from post-procedure pain scores in a randomized controlled trial of stress ball use during unsedated endoscopy (Karatas & Gezginci, 2023), was used as the reference effect size. This study was selected as the closest available proxy given its use of the same intervention in a comparable invasive procedural context.

The calculation indicated that 64 participants (32 per group) would be required to detect the reference effect. Allowing for an anticipated 10% attrition rate, the target enrollment was set at 74 participants (37 per group). The acknowledged limitation that the reference effect size derives from a subjective pain outcome rather than an HRV-specific endpoint is discussed in the limitations section of the primary publication.

5. Analysis Populations

The following analysis populations are defined for this analysis:

Population	Definition
Full Analysis Set / ITT	All randomized participants, analyzed according to the group to which they were randomized regardless of intervention received. The FAS is the primary analysis population for all efficacy endpoints.
Per-Protocol Set	Participants in the FAS who: (a) received the allocated intervention as specified, (b) had no major protocol deviations, and (c) had complete primary outcome data with intraoperative HRV recordings meeting the R-wave validity criterion ($\geq 75\%$ valid beats). Used in supportive sensitivity

	analyses.
Safety Set	All randomized participants who underwent the surgical procedure, analyzed by the intervention actually received. Used for descriptive safety reporting only.

Major protocol deviations include: receipt of a non-allocated intervention, conversion to general or regional anesthesia, unplanned use of anxiolytic or sedative medication during the perioperative window, and HRV recording with < 75% valid R-waves.

6. Endpoints

6.1 Primary Endpoint

(Prospectively specified in the ClinicalTrials.gov registration as “Heart Rate Variability”).

Intraoperative HRV, operationalized as the natural log-transformed root mean square of successive differences (lnRMSSD), recorded continuously during the surgical procedure (T2) with the participant in the supine position.

HRV Acquisition and Preprocessing

- Device: portable ECG recorder (Amor HRV Guard, model 8z05; Leadtek Research Inc., Taiwan).
- Sampling rate: 500 Hz.
- Recording position: supine throughout the surgical procedure.
- Validity criterion: a minimum R-wave validity of 75% is required for inclusion in the primary analysis. RMSSD remains valid when up to 36% of beat-to-beat intervals are removed (Sheridan et al., 2020); the 75% threshold provides a conservative margin appropriate to the intraoperative environment.
- Transformation: because raw RMSSD values are typically right-skewed, a natural logarithmic transformation is applied prior to all analyses, in accordance with Laborde et al. (2017). The transformed variable, lnRMSSD, is used in all subsequent analyses.

6.2 Secondary Endpoints

(Prospectively specified in the ClinicalTrials.gov registration.)

- Postoperative state anxiety, assessed by the Mandarin-Chinese version of the State-Trait Anxiety Inventory-State subscale (STAI-State; Ma et al., 2013), administered at T3 (immediately postoperative).
- Postoperative pain intensity at the surgical site, assessed by a 10-cm Visual Analogue Scale (VAS; Myles et al., 2017), administered at T3.

6.3 Baseline (T1) Measurements

Baseline (T1) measurements include a 5-minute resting HRV recording (seated), STAI-State, and VAS, all collected on the day of surgery prior to the procedure. T1 values for each outcome are used as covariates in the corresponding analyses.

6.4 Other Variables

Demographic and clinical characteristics collected at baseline include age, sex, BMI, education level, marital status, type of surgical procedure, and relevant medical history (hypertension, diabetes, kidney disease, depression, anxiety, cancer).

7. Estimand Framework (ICH E9(R1))

The estimand for the primary endpoint is defined as follows:

Attribute	Specification
Treatment	Intraoperative rhythmic stress-ball squeezing throughout the surgical procedure (IG) versus standard perioperative nursing care without stress ball (CG).
Population	Adult patients undergoing outpatient hand surgery under local anesthesia without sedation who satisfy the eligibility criteria.
Variable	Intraoperative lnRMSSD measured continuously during the surgical procedure.
Intercurrent Events	(a) Conversion to general or regional anesthesia — treatment-policy strategy. (b) Unplanned anxiolytic or sedative use — treatment-policy strategy. (c) Premature termination of the procedure — while-on-treatment strategy. (d) HRV signal artifact — handled by the 75% R-wave validity criterion (see Section 10).
Population-level Summary	Conditional on the homogeneity-of-slopes test (see Section 9.3): if the assumption holds, the adjusted between-group difference in mean intraoperative lnRMSSD with 95% CI; if violated, the regions of significance from the Johnson–Neyman procedure across baseline lnRMSSD values.

8. General Statistical Considerations

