9.3 Primary Analysis (Conditional on Homogeneity-of-Slopes Test)

The primary analysis examines intraoperative lnRMSSD using a regression model that includes group, baseline lnRMSSD, the Group \times Baseline lnRMSSD interaction term, age, and sex. The homogeneity of regression slopes assumption is evaluated by the significance of the Group \times Baseline lnRMSSD interaction term. The analysis path is conditional on this test:

Path A — Interaction not significant ($p \geq .05$)

If the homogeneity-of-slopes assumption holds, the interaction term is removed and a standard ANCOVA is fitted:

$$\ln\text{RMSSD_T2} = \beta_0 + \beta_1 \times \text{Group} + \beta_2 \times \ln\text{RMSSD_T1} + \beta_3 \times \text{Age} + \beta_4 \times \text{Sex} + \epsilon$$

Results are reported as adjusted means (SE) per group, the adjusted between-group mean difference (IG – CG) with 95% CI, the F-statistic with degrees of freedom, p-value, and partial eta squared (η^2).

Path B — Interaction significant ($p < .05$)

If the homogeneity-of-slopes assumption is violated, the conditional treatment effect across the range of baseline lnRMSSD values is examined using the Johnson–Neyman (J–N) procedure (Hayes, 2022; Ji, 2016) — the standard methodological response to violation of the homogeneity-of-slopes assumption when the moderating variable is continuous. The full moderation model is retained:

$$\text{lnRMSSD_T2} = \beta_0 + \beta_1 \times \text{Group} + \beta_2 \times \text{lnRMSSD_T1} + \beta_3 \times (\text{Group} \times \text{lnRMSSD_T1}) + \beta_4 \times \text{Age} + \beta_5 \times \text{Sex} + \epsilon$$

Results are reported as: (i) the overall model F-statistic and R^2 ; (ii) the Group \times Baseline lnRMSSD interaction F-statistic, p-value, and ΔR^2 ; (iii) the J–N region(s) of significance; and (iv) the proportion of the analyzed sample that falls within each region. Conditional simple effects are plotted across the observed range of baseline lnRMSSD.

The primary analysis is performed in the FAS (ITT).

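### On Path B the primary analysis and the estimand contain no average treatment effect and no rule for judging H1; the only overall comparison is an unadjusted sensitivity test

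*Combined protocol and SAP*

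**What the plan says.** The primary objective in Section 2.1 is "To evaluate the effect of intraoperative stress ball use on intraoperative HRV" against standard care. Section 2.3 gives it a direction without any condition on baseline: "H1 (Primary): Higher intraoperative lnRMSSD, reflecting enhanced parasympathetic modulation". Section 4 sizes the trial for an overall two-group difference (d = 0.71, two-sided alpha 0.05, power 0.80).

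Section 7 does not fix one population-level summary. If the Group × Baseline interaction is not significant, the summary is the adjusted between-group difference with 95% CI; "if violated, the regions of significance from the Johnson–Neyman procedure across baseline lnRMSSD values".

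Section 9.3 follows the same split. Path A reports adjusted means, the IG – CG difference with 95% CI, F, p and partial eta squared. On Path B, "The full moderation model is retained", and the listed results are the model F and R², the interaction F, p and ΔR², the Johnson–Neyman regions, and the share of the sample in each. Conditional effects are also plotted over the observed baseline range.

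Section 9.5 plans, on either path, an unadjusted t-test or Mann–Whitney U on T2 lnRMSSD as a sensitivity analysis. Section 14 describes the Johnson–Neyman step as a response to a slope violation that was observed, and lists ANCOVA as the base framework in the IRB-approved protocol.

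**The concern.** The objective, H1 and the sample size all pose one question: does stress-ball use raise lnRMSSD on average in the trial population? On Path B the primary analysis answers a different one: at which baseline values does the conditional difference reach p < .05? Three problems follow.

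- The estimand is selected by a test on the trial's own data, so it is not fixed in advance.
- The replacement summary depends on sample size and alpha. Two trials of the same treatment in the same population, but of different size, would be aiming at different regions.
- No decision rule is given. If one region favours IG and another favours CG, the plan does not say whether H1 is supported.

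Because Section 14 indicates that this branch applies, the registered directional hypothesis stands to be reported without a confirmatory estimate, and a region favouring IG could be read as support for it.

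**Working it through.** **1. What each section delivers**

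| Item | Path A | Path B |
|---|---|---|
| Section 7 summary | Adjusted mean difference, 95% CI | Regions of significance |
| Average IG – CG difference in the primary analysis | Yes | Not listed |
| Rule for H1 | Not spelled out, but the group test addresses it directly | None |
| Unadjusted overall test (Section 9.5) | Sensitivity only | Sensitivity only |
| Per-protocol and covariate-minimal analyses (Section 9.5) | Repeat Path A | Repeat Path B |

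**2. The plan's own figure**

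Inputs from Section 4: d = 0.71, two-sided alpha 0.05, power 0.80. Normal approximation per arm: 2 × (1.960 + 0.842)² / 0.71² = 2 × 7.85 / 0.504 = 31.1, rounded up to 32. This matches "64 participants (32 per group) would be required to detect the reference effect". (Noncentral t gives 33 per arm, and 33 / 0.9 = 36.7, rounded up to 37, matches the enrolment target of 74.) The sample size is not in dispute. It confirms that the trial was sized for an overall two-group difference, not for an interaction or a region.

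**3. The region moves with sample size**

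Assumptions, not in the documents: baseline standardised, residual SD 1, average effect 0.3, slope difference −0.6, regions read within ±2.5 SD of the baseline mean. The conditional effect at baseline x is 0.3 − 0.6x, with variance (4/N)(1 + x²). The boundaries solve (0.3 − 0.6x)² = t² (4/N)(1 + x²).

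At N = 74, t ≈ 1.995 and t² × 4/74 ≈ 0.215. This gives 0.145x² − 0.36x − 0.125 = 0, with roots near −0.31 and +2.8. The second lies outside the range. The same step at other sizes gives:

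| N | IG-favouring region | CG-favouring region |
|---|---|---|
| 74 | below −0.31 SD (38% of patients) | none in range |
| 148 | below −0.04 SD (48%) | above +1.46 SD (7%) |
| 740 | below +0.25 SD (60%) | above +0.81 SD (21%) |

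The true effects are identical in every row. Only N changes.

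**4. How often Path B yields a favourable region when the average effect is zero**

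Simulation of the Section 9.3 rule. Assumptions, not in the documents: 37 per arm, baseline SD 1, average effect zero, regions limited to observed baseline values.

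| Slope difference | Residual SD | Path B entered | IG-favouring region | Regions both ways |
|---|---|---|---|---|
| 0.5 | 0.87 | 66% | 55% | 46% |
| 0.5 | 1 | 52% | 42% | 33% |
| 0.2 | 0.87 | 16% | 12% | 7% |

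Repeat runs differ by a percentage point or two. The no-interaction ANCOVA test of the average effect rejects in about 5% throughout.

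A rough check on the entry rates: the standard error of the slope difference is about 2 × SD / √74. That is 0.2325 at SD 1 and 0.2023 at SD 0.87. The ratios 0.5/0.2325 = 2.15, 0.5/0.2023 = 2.47 and 0.2/0.2023 = 0.99 imply power of about 56%, 68% and 16%. The first two are slightly above the simulated values because the formula ignores random variation in the sampled baselines.

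**5. Can the planned size support the average effect?**

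At N = 74 the 95% CI half-width is about 1.995 × 2/√74 = 0.46 residual SD. Power at a standardised difference of 0.71 is about 85%. It can.

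**The case against.** The strongest reply is that the plan does keep an overall comparison. Section 9.5 tests T2 lnRMSSD between arms whichever path is taken, Section 8.2 sets intervals at 95%, Section 15 commits the publication to reporting sensitivity analyses, and randomisation makes the unadjusted contrast a fair estimate of the average effect. This stands, and it limits the point. A reader might infer that the plan never reports an overall effect; the documents do not support that. What remains is status: the test is a sensitivity analysis, omits baseline adjustment, may be replaced by a rank test that gives no mean difference, is not the Section 7 estimand, and has no stated role for H1.

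Path B also plots conditional effects, so it shows more than significance boundaries. That is true, but a plot of conditional effects is still not an average.

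A reader might treat the 42–55% as a false-positive rate. It is not one. In those scenarios the conditional effects really are non-zero away from the mean, and the ANCOVA test addresses a different hypothesis. The figures also fall sharply with a smaller slope difference.

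Finally, because baseline is not centred in the Path B model, the Group coefficient is the effect at lnRMSSD = 0, that is RMSSD = 1 ms. A reader might suspect it would be presented as the overall effect. The plan does not list it for reporting, so this is only a caution for implementation.

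**Conclusion.** The point holds for the primary analysis and the estimand. On Path B neither contains an average treatment effect or a rule for H1, although the objective, the hypothesis and the sample size are all about an average effect. The population-level summary is chosen by a test on the trial data, and its Path B form is not a fixed population quantity. This rests on the text of Sections 2, 4, 7 and 9.3, and on Section 14 for Path B being the branch in use.

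The size is illustrative only. With zero average effect and 37 per arm, an IG-favouring region appears in about 42–55% of trials at slope difference 0.5 and about 12% at 0.2, under the assumed SDs; the documents give no slopes or SDs. These figures show that the region and H1 are different questions. They say nothing about this trial's actual result.

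**What to change.** - **Section 7:** define one population-level summary for all cases: the adjusted IG – CG difference in mean lnRMSSD with 95% CI.
- **Section 9.3:** report that difference on both paths from the ANCOVA without interaction, which Section 14 lists as the IRB-approved base framework. State that H1 is judged only on it and that Johnson–Neyman results describe heterogeneity. Because "Participants are randomly allocated 1:1", this model can still target the average effect when slopes differ; its rejection rate stayed at about 5% in the simulations above.
- **If the interaction model is preferred for the average effect:** centre baseline lnRMSSD at the sample mean and use a standard error that allows for that mean being estimated. Without the allowance, the centred test rejected in about 6.4% of simulated trials with zero average effect and slope difference −0.6.
- **Section 14:** record that this clarification was made after the slope violation was observed, so that it is not read as prespecified.

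The cost is SAP wording and one extra row in the results table, with no new data. The real concession is that the Johnson–Neyman regions lose primary status.
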